5.0 Study Procedures

After proper informed consent and/or assent have been obtained, all patients will receive a general anesthesia using standard of care. For all patients randomized to receive regional nerve block (Group A & C) a time out before regional anesthesia will be performed stating patient identification and proposed surgical procedure with location of the block to be performed and the medications to be injected.

Patients randomized to receive regional anesthesia will be prepared following standard universal precautions with application of sterile cleaning solution of chlorhexidine (Chloraprep) or alcohol prior to injections.

The site of local anesthetic injection will be identified according to the landmarks defined by their respective anatomical descriptions. The nerve of Arnold block is located at junction of the ear tragus and external 1/3 of ear canal which will be injected using a 30 G needle with 0.5 ml of Bupivacaine 0.25%. na

The Superficial Cervical Plexus located at Erb's Point, posterior border of the sternocleidomastoid muscle and a bisecting horizontal line drawn from the cricoid cartilage at the level of the sixth vertebrae, which is slightly posterior to the external jugular vein, this site will be injected with 3-5ml of bupivacaine 0.25% with 1:200000 of epinephrine. Surgical procedures lasting longer than 4hrs will require a repeat injection with 2.5-3 ml of bupivacaine 0.25% with 1:200000 epinephrine at this latter location after completion of the surgical procedure prior emergence from anesthesia.

Group A: to receive a homolateral (same side) to surgical site or bilateral if surgery involves both ears regional block at the Erb's point and Nerve of Arnold.

The block will be performed prior to surgical incision and may be repeated at Erb's point only with half the initial volume of local anesthetic (1.5 ml -2.5ml) at completion of surgery prior emergence from anesthesia, if the procedure lasted more than 4 hours after the initial block.

Group B: will receive an anti-emetic drug regiment comprising of dexamethasone 150mcg/kg IV (max dose of 10 mg) and ondansetron 150mc/kg IV (max single dose of 4 mg) at any time after induction of anesthesia and as soon as an intravenous line is available. If, at the anesthesiologist's discretion, ondansetron is re-dose at the end of procedure, a max total dose of 8 mg may be given.

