Group C: Will receive both a homolateral or bilateral if surgery involves both ears, a regional block at Erb's point (superficial cervical plexus block) and will receive an anti-emetic drug regiment comprising of dexamethasone 150mcg/kg IV (max dose of 10 mg) and ondansetron 150mc/kg IV (max single dose of 4 mg) at any time after induction of anesthesia and as soon as an intravenous line is available. If, at the anesthesiologist's discretion, ondansetron is re-dose at the end of procedure, a max total dose of 8 mg may be given.

All three groups will receive a standardized general anesthetic regiment, prior to induction the patient *might* require an oral dose of versed 0.5mg/kg as premedication for separation anxiety. Patients will also receive induction of anesthesia either inhalational oxygen in sevoflurane or intravenous induction if subject patient has an IV access, muscle relaxants will be avoided to preserve facial nerve monitoring as required by the surgical approach. Anesthesia will be maintained with oxygen in sevoflurane or desflurane. Prior to emergence of anesthesia and at any point during the procedure, patients may receive IV analgesics (acetaminophen, morphine, fentanyl, ketamine) for postoperative analgesia according to the standard recommended pediatric dosing regiments commonly used at Riley Hospital.

All three groups will receive the standard PACU protocol for pain management and anti-nausea and vomiting intervention. Following patient's recovery starting upon emergence (t_0), all symptoms indicating nausea and/or vomiting and pain will be recorded and every 15min (t_{15}) thereafter in PACU than every 4-6 hrs. while on the inpatient unit for 24 hrs and will be treated as deemed necessary. For pain assessment a FLACC scale and Visual Analogue Scale (VAS) will be used. Complaints of, or signs or symptoms of, nausea, retching and/or vomiting will be documented in the PACU or floor for 24 hours post-operatively. For patients discharged to home prior to the 24 hours, follow up will be done by phone call using the Rhodes INRV to report post-operative nausea and vomiting.

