We will also review patients chart for requests or demands for any pain medications and anti-emetics, documentation of their usage as well as times of discharge from the recovery room to the floor and their discharge from the hospital. For cost comparison and analysis we will look at itemized billing for medical services related to anesthesia, pharmacy use and IV fluid use, antiemetic interventions, medication for pain throughout hospital stay from recovery room to time of discharge from the hospital. For patients that are discharged the same day of their surgery they will be given The Rhodes INRV survey to fill out at home and will be called by phone the following day to collect that information.

A cost analysis between the three study groups taking into account all the items above will be done to compare overall cost of care between the three study groups.

6.0 Reporting of Adverse Events or Unanticipated Problems Involving Risk to Participants or Others

Risk related to the Blocks

Bleeding

Infection at the site

Intravascular local anesthetic injection

Anaphylactic/allergic reaction

Rare spread of local to deeper structures, inadvertent Phrenic nerve blockade (the injection are superficial, subcutaneous with specific landmarks)

Failure of the block to produce pain relief or to prevent nausea and vomiting

Complications related to the surgical procedure including but not limited to:

Facial nerve blockade

Risk of General Anesthesia

All precautions will be taken care of to avoid the above complications by adhering to standard of practice with strict adherence to standard ASA monitoring will be used at all time, observance of the time out procedure and surgical site marking, using universal precautions for sterility and observance of safe injection technique for the regional blocks with intermittent aspiration and injection to avoid intravascular injection and use of live imaging with ultrasound guidance if necessary.

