8.0 Statistical Considerations

A sample size of 20 subjects per group was selected to provide 80% power for finding a difference between all three groups with nausea/vomiting of 90% vs. 50%, assuming two-sided chi-square tests conducted at a 5% significance level. At completion of study we will submit our data to statistical analysis.

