1. Great auricular nerve
 2. Lesser occipital nerve
 3. Auricular branch of vagus nerve
 4. Auriculotemporal nerve

[figure not shown]
Ear Innervation

Superficial Cervical Plexus Anatomical Relations and Injection Site

Vagus Nerve (X)

RHODES INDEX OF NAUSEA, VOMITING AND RETCHING

Patient initials _____

Date _____

[figure not shown]
Day of week _____

Time of day _____

[figure not shown]
Directions: Please mark the box in each row that most clearly corresponds to your experience. Please make **one** mark on **each line**.

1. In the last 12 hours, I threw up ____ times.	7 or more	5-6	3-4	1-2	I did not throw up
2. In the last 12 hours, from retching and dry heaves, I have felt ____ distress.	no	mild	moderate	great	severe
3. In the last 12 hours, from vomiting or throwing up, I have felt ____ distress.	severe	great	moderate	mild	no
4. In the last 12 hours, I have felt nauseated or sick to my stomach.	not at all	1 hour or less	2-3 hours	4-6 hours	more than 6 hours
5. In the last 12 hours, from nausea/sickness to my stomach, I have felt ____ distress.	no	mild	moderate	great	severe
6. In the last 12 hours, each time I threw up, I produced a ____ amount.	very large (3 cups or more)	large (2-3 cups)	moderate (1/2-2 cups)	small (up to 1/2 cup)	I did not throw up
7. In the last 12 hours, I have felt nauseated or sick to my stomach ____ times.	7 or more	5-6	3-4	1-2	no
8. In the last 12 hours, I have had periods of retching or dry heaves without bringing anything up ____ times.	no	1-2	3-4	5-6	7 or more

Copyright 1996. Curators of Missouri. [name], EdS, FAAN

Superficial cervical Plexus infiltration

Nerve of Arnold Injection

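### No masking of families, ward recorders or the next-day caller is described for a partly subjective outcome; withholding the group from families until 24 hours is a cheap, partial remedy

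*Combined protocol and SAP*

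**What the plan says.** Section 4.0 assigns children to three groups by a computer program: block (A), IV antiemetics (B), or both (C). It does not say who then learns the assignment.

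Section 5.0 covers outcome collection. In hospital, "Complaints of, or signs or symptoms of, nausea, retching and/or vomiting will be documented in the PACU or floor for 24 hours post-operatively". Checks start at emergence, run every 15 minutes in PACU and then every 4 to 6 hours on the unit; the recorder is not named. For children who leave before 24 hours, "follow up will be done by phone call using the Rhodes INRV to report post-operative nausea and vomiting". Same-day patients are "given The Rhodes INRV survey to fill out at home and will be called by phone the following day to collect that information".

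The appended Rhodes form asks separately about vomiting ("In the last 12 hours, I threw up", item 1), retching ("I have had periods of retching or dry heaves without bringing anything up", item 8) and nausea ("from nausea/sickness to my stomach, I have felt", item 5), all in the respondent's own words.

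Section 8.0 sizes the trial at 20 per group for "finding a difference between all three groups with nausea/vomiting of 90% vs. 50" (both figures are percentages), using two-sided chi-square tests at 5%. The composite is not defined further.

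On timing, section 5.0 gives the IV antiemetics in groups B and C "at any time after induction of anesthesia and as soon as an intravenous line is available". The group A text places the block before incision and any repeat before emergence. The section describes general anesthesia first and the block after it. This implies, but does not state, that the child is already asleep for the first block.

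The only mention of blinding is in the title of a cited study in the reference list.

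**The concern.** The regimens differ visibly, no sham or placebo is described, and families know from consent that a block is being compared with drugs. A parent or nurse who knows the group may be readier, or less ready, to call a fussy child nauseated. For children at home the same applies to reported vomiting and retching, because nobody from the study team observes them.

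All three arms are active treatments, so neither the direction of any shift nor the comparison most affected can be predicted. The arms are small: one reclassified child in 20 is 1/20 = 5 percentage points. The documents do not give the share of events that are nausea only, or the share of children discharged before 24 hours.

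The protocol's own timing seems to allow a simple protection that it does not use. If drugs and block are all given under anesthesia, a family need not know the group before the outcome is collected.

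**Working it through.** **The plan's own figure.** Inputs from section 8.0: p1 = 0.90, p2 = 0.50, two-sided alpha 0.05, power 0.80; mean rate 0.70.

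n = [1.960 × √(2 × 0.70 × 0.30) + 0.842 × √(0.90 × 0.10 + 0.50 × 0.50)]² / 0.40² = (1.270 + 0.491)² / 0.16 = 19.4, so 20 per group.

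The stated 20 is reproduced for one pairwise comparison without continuity correction. The normal approximation gives 81.3% power at n = 20. Exact enumeration of the uncorrected Pearson chi-square gives 83.8%, which is the reference below. Masking does not enter the formula.

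**Illustration of differential reporting.** Assumptions, not from the documents: a share f of events is nausea only, and a share u of those goes unreported in one arm. Then

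recorded rate = true rate × (1 − f × u).

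Example: 0.90 × (1 − 0.50 × 0.20) = 0.81, a shift of 9 points, or 20 × 0.09 = 1.8 children. The 90% and 50% rates are the plan's; 70% is their midpoint. Each cell is the exact rejection probability with 20 per arm and no true difference:

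| True rate, both arms | No loss | u = 0.10, f = 0.25 | u = 0.10, f = 0.50 | u = 0.20, f = 0.25 | u = 0.20, f = 0.50 |
|---|---|---|---|---|---|
| 90% | 3.9% | 4.8% | 6.5% | 6.5% | 12.2% |
| 70% | 5.3% | 5.5% | 6.0% | 6.0% | 7.9% |
| 50% | 4.3% | 4.3% | 4.5% | 4.5% | 5.3% |

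**Equal loss in both arms.** At a 90% rate with u = 0.20, the false-positive rate is 4.9% (f = 0.25) or 5.0% (f = 0.50). The inflation therefore comes from the loss being in one arm only.

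**Power at a true 90% vs 50%, u = 0.20:**

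| Where the loss falls | f = 0.25 | f = 0.50 |
|---|---|---|
| Nowhere | 83.8% | 83.8% |
| Higher-rate arm only | 70.9% | 56.4% |
| Lower-rate arm only | 87.6% | 90.7% |
| Both arms equally | 76.2% | 67.9% |

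Part of the fall in the second row is due to under-reporting as such, which masking would not cure.

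**Vomiting/retching on its own.** The plan gives no rate for it. Keeping the plan's ratio (50/90 = 0.556) at assumed lower rates, exact power with 20 per group is 67% at 80% vs 44% and 17% at 30% vs 17%. It can support the composite but not replace it.

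**The case against.** The strongest objection is that the fix leaves the main route open. In-hospital events are recorded by staff who may know the group and who talk to the family. Eligibility starts at age 1, so in the youngest children nausea rests on signs judged by others, and keeping the group from parents changes little there. This stands: the remedy is partial.

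The illustration is also narrower than the worry. It models under-reporting only, of nausea only, in one arm only. The 12.2% is its most extreme null cell. A reader might infer that the trial's error rate will be about 12%, or that masking families would bring it back to 5%. The documents support neither: they give no size for reporting bias, no nausea-only share and no share of children at home. The figures cover loss through any route, including the staff route that stays open.

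A reader might also infer that the result would favor the block. With three active arms, nothing in the documents fixes the direction.

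The silence may not be complete. Consent pages and figures are not in the public text, and what families are told could be stated there. Sections 4.0 and 5.0 are present and silent, which lowers confidence but does not remove the point.

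Finally, comparing visibly different regimens openly is a legitimate choice for a trial of therapeutic and cost effectiveness, and no passage contradicts another. That is why this is an improvement to the design, not an error in it. Separate symptom data largely exist already, since the Rhodes form and section 5.0 name the symptoms individually; what is missing is a commitment to report them that way.

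**Conclusion.** The point holds as a recommended improvement, with medium confidence. The available text describes no masking of families, PACU or floor recorders, or the next-day caller, while the powered composite includes nausea that is self-reported or judged from signs. For children at home, vomiting and retching are family-reported as well.

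The possible harm ranges from negligible to material. Under the 1-in-5, one-arm assumption it is about one percentage point or less of false-positive rate when the event rate is 50%, and 2.6 to 8.3 points when it is 90% (6.5 − 3.9 and 12.2 − 3.9). How much of any such bias the change would remove cannot be computed from the documents. The case for it rests on its low cost. Its feasibility rests on the first block being given after induction, which section 5.0 implies and should state.

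**What to change.** Add to section 5.0:

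1. The child and parents are not told the group until the 24-hour outcome, including any home Rhodes form, has been collected, unless this is needed for care. Any earlier disclosure is recorded. Treating clinicians keep full access to what was given.
2. Where an existing team member without access to the allocation is available, that person makes the next-day call. This adds little when the form is already complete. It matters more when the form was not completed, or when the phone call is the only follow-up.
3. As a supportive analysis only, vomiting/retching is reported separately from nausea, with each event marked as staff-observed or home-reported.

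The protocol should also state whether the first block follows induction, because item 1 depends on it. Saying openly that PACU and floor recording is unmasked helps readers but changes no result.

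Cost: protocol wording, a record of early disclosures and one source mark per event. No patients, visits or instruments are added, and the powered composite and 20 per group do not change. Whether a caller can be kept from the allocation must be checked locally, so item 2 is optional.

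Downside: masking is partial. PACU and floor staff stay unmasked, and numbness, injection marks or use of the care exception may reveal the group.

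### The protocol names harms of the nerve block but plans no systematic collection of any harm, so a reported zero could not be told apart from unrecorded events

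*Combined protocol and SAP*

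**What the plan says.** Section 6.0 is headed as the adverse-event section. Under "Risk related to the Blocks" it lists bleeding, "Infection at the site", intravascular injection, allergic reaction, spread to deeper structures with phrenic nerve blockade, and "Failure of the block to produce pain relief or to prevent nausea and vomiting". It then mentions surgical complications, facial nerve blockade and the risk of general anesthesia, and closes with precautions. It gives no form, schedule, assessor or grading. It names no harm of dexamethasone or ondansetron, the drugs given in Groups B and C; the only related text is the allergy exclusion in section 3.0.

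Section 5.0 sets the observations. From emergence, "all symptoms indicating nausea and/or vomiting and pain will be recorded and every 15min" in PACU, then every 4-6 hours on the ward up to 24 hours. On emetic symptoms it adds: "Complaints of, or signs or symptoms of, nausea, retching and/or vomiting will be documented in the PACU or floor for 24 hours post-operatively". For children who leave before 24 hours, "follow up will be done by phone call using the Rhodes INRV to report post-operative nausea and vomiting". Those who go home on the day of surgery "will be called by phone the following day to collect that information". Chart review covers analgesic and antiemetic requests and use, and discharge times. Billing review covers cost items up to hospital discharge.

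Section 7.0 discontinues the study and notifies the IRB if an unanticipated adverse event with a known direct relation to the procedure occurs. It does not say how such an event would be found.

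**The concern.** The trial sets a needle procedure against two intravenous drugs in children. A reader of the results will want to know what harm came with each. The protocol recognises several harms of the block but attaches none of them to a scheduled observation, and it lists no harm of the drugs. A harm that nobody asks about at the last contact cannot be recovered at analysis.

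A report of no bleeding, no infection and no drug reactions would then be hard to interpret: it could mean that none occurred or that none were written down. The gap is widest for children who go home the same day, because their one later contact collects an emesis questionnaire. The section 7.0 rule is affected too, since it acts on events that no planned data source supplies.

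**Working it through.** **1. The plan's own figure.** The plan gives no number for harms. Its only sample-size figure is for efficacy (section 8.0): 20 per group, 80% power, 90% vs 50%, two-sided chi-square at 5%. With mean rate 0.70 and no continuity correction:

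n = [1.960 × √(2 × 0.70 × 0.30) + 0.842 × √(0.90 × 0.10 + 0.50 × 0.50)]² / 0.40² = (1.270 + 0.491)² / 0.16 = 19.4, so 20 per group. Power at 20 is 81.3%.

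The figure reproduces. The present point does not depend on it, except that it fixes 20 per group, hence 40 children with a block (A + C) and 40 with the study drugs (B + C).

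**2. Each planned data source, set against the harms.**

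| Source | What it records | Runs until | Harm item |
|---|---|---|---|
| PACU and ward checks (5.0) | Nausea/vomiting, pain | 24 h | None named |
| Chart review (5.0) | Analgesic and antiemetic requests and use, discharge times | Hospital discharge | None named |
| Billing review (5.0) | Cost items | Hospital discharge | None named |
| Call after same-day discharge (5.0) | Rhodes form | Following day | None |
| Section 7.0 | Unanticipated procedure-related events | Not stated | Action given, no source |

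The Rhodes form in the appendix has 8 items: three on vomiting (for example "In the last 12 hours, each time I threw up, I produced a" with a volume to tick), two on retching and three on nausea. 3 + 2 + 3 = 8, which leaves none for the injection site, bleeding, breathing, facial movement or a drug reaction.

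Section 7.0 does not fill the gap. Bleeding and infection are already listed in section 6.0, so they are arguably anticipated and fall outside its wording.

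**3. What a zero would mean.** Let s be the fraction of true events that gets recorded. The documents give no value, so s is an assumption, shown over a range. After zero recorded events in n children, the exact one-sided 95% upper limit on the true rate is [1 − 0.05^(1/n)] / s. With complete collection (s = 1):

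- n = 40: 1 − 0.05^(1/40) = 7.2% (two-sided exact limit 8.8%)
- n = 20: 1 − 0.05^(1/20) = 13.9% (two-sided exact limit 16.8%)

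For n = 40 and other values of s, with the chance of recording no event when the true rate is 5% (also assumed), which is (1 − 0.05 × s)^40:

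| s | Upper limit after 0/40 | Chance of recording zero |
|---|---|---|
| 1 | 7.2% | 13% |
| 0.5 | 14.4% | 36% |
| 0.25 | 28.9% | 61% |
| 0.1 | 72% | 82% |

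Nothing in the plan tells the reader which row applies.

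**The case against.** The strongest reply is that harms would not go unseen. The injections are superficial, standard ASA monitoring applies throughout, children are checked every 15 minutes in PACU and every 4-6 hours on the ward, and section 5.0 does not forbid noting other events. Section 10.0 mentions data collection sheets that are not shown. The two drugs are described as usual prophylaxis, and the stated aims are therapeutic and cost effectiveness, so no comparison of harms is promised. Even perfect recording in 40 children leaves an upper limit of 7.2%.

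Much of this stands. An intravascular injection, an acute reaction or bleeding in hospital could well be noticed. A reader might infer that infection and bleeding must come out as zero in Groups A and C; the documents do not support that. What they show is that such events are not systematically sought. Nor do they give an onset time for site infection, so the point does not rest on one. It is enough that no contact is planned after the next-day call for a child who went home on the day of surgery.

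A reader might also see that failure to prevent nausea and vomiting is listed as a block risk, apply the section 8.0 rates to 20 children (20 × 0.50 = 10, 20 × 0.90 = 18), and infer that 10 to 18 children per block arm would count as harmed, against none in Group B. That does not follow. Section 6.0 is a statement of risks, nowhere tallied by arm, and section 8.0 does not assign the two rates to arms.

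What the reply leaves unanswered is that noticing an event in care is not the same as recording it alike in three groups.

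**Conclusion.** The point holds in this form: no section provides for systematic collection of any harm, no study-drug harm is listed, and the only contact after a same-day discharge has no harm item. A reported zero, especially after discharge, could not be told apart from unrecorded events. In numbers, 0/40 would exclude true rates above 7.2% with complete collection, but only above 28.9% if a quarter of events were captured and 72% if a tenth were. Those capture fractions are assumptions; the documents give none.

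The efficacy comparison is untouched. The plan contains no biased harm comparison, because it contains no harm comparison at all. The change is still worth making before enrollment, since it is cheap and the information cannot be recovered later.

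**What to change.** - Use one short adverse-event checklist, identical in all three groups, covering the section 6.0 items plus reactions to dexamethasone and ondansetron. State who completes it. Group B, which has the surgery without the block, then gives a reference for events that surgery itself may cause.
- Complete it at PACU discharge and again at the existing 24-hour ward check or next-day call.
- If a routine postoperative visit exists (an assumption; the documents mention none), extend the chart review to that visit for site infection and bleeding.
- Treat failure to prevent nausea and vomiting as an efficacy outcome only, and take it off the harm list.
- Report counts by group with exact confidence limits, as description and not as a test between arms.

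The cost is one form, a few added questions at contacts already planned, slightly more data entry, and possibly a later database close. No treatment, dose or sample size changes.

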1.0 Background

Patients that undergo inner ear surgery often complain of postoperative nausea and vomiting (PONV) despite prophylactic antiemetic regimens with 5HT3 antagonists, steroids and vigorous hydration. Patients still experience this unpleasant feeling that may prolong hospital stay and can lead to nutritional issues such as dehydration and huge patient and family dissatisfaction. We would like to explore the use of regional anesthesia and potential antiemetic properties and compare its efficacy to the existing therapy.

PONV is an unpleasant complication following anesthesia, it is well known that patients undergoing certain surgical procedures such as those involving the inner ear, the tympanomastoid cells, and the cochlear organ may be more prone to PONV. This complication can be anticipated in those instances and prophylactically treated with antiemetics, Vigorous hydration and cautious selection of anesthetic technique and avoidance of drugs known to promote nausea^{1,2,3}. Despite all the measures described above, vomiting still occurs often, leaving patients and their families wondering if more can be done^{4,5}.

Regional anesthesia has a therapeutic and preventive role in the incidence of PONV by reducing post-operative pain and opioids consumption.

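### Children sent home before 24 hours are followed with a form that looks back 12 hours, at an unstated hour, so the 24-hour nausea and vomiting window is not ensured

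*Combined protocol and SAP*

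**What the plan says.** Section 5.0 records symptoms from emergence, every 15 minutes in the recovery room and then every 4–6 hours on the ward. It states that nausea, retching and vomiting "will be documented in the PACU or floor for 24 hours post-operatively".

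Two sentences in the same section cover children who leave sooner:

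- Any discharge before 24 hours: "For patients discharged to home prior to the 24 hours, follow up will be done by phone call using the Rhodes INRV". No day or hour is given for the call.
- Same-day discharge only: "they will be given The Rhodes INRV survey to fill out at home and will be called by phone the following day". This gives the day of the call but no hour, and no time for completing the form.

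The Rhodes form is reproduced after the references. All eight items share one recall period, for example "In the last 12 hours, I have felt nauseated or sick to my stomach". The form has date and time-of-day fields, so it could be used more than once, but nothing schedules repeat use.

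Section 8.0 plans 20 children per group for 80% power at 90% vs 50% nausea/vomiting, with a two-sided 5% chi-square test. It does not tie those rates to a time window.

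**The concern.** A 24-hour outcome is to be measured, in early discharges, with a 12-hour instrument at an unspecified time. Children who stay 24 hours are charted throughout, while children who leave early may have hours that nobody asks about. A child discharged the next morning but before hour 24 falls outside the same-day sentence and has only the undated call.

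A case is lost only if nothing is charted before discharge, nothing falls in the form's 12 hours, and the only episodes fall in the gap. Such losses lower the observed rates. If they are similar in two arms, the difference shrinks and power falls. If they differ, the comparison can be biased in either direction.

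Unequal losses could come from different discharge times or different episode times by arm. The documents make both conceivable and show neither. Section 1.0 says of postoperative nausea and vomiting: "Patients still experience this unpleasant feeling that may prolong hospital stay". Section 5.0 treats the block as limited in duration: "Surgical procedures lasting longer than 4hrs will require a repeat injection".

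**Working it through.** **Plan's own figure.** For 90% vs 50%, two-sided 5%, 80% power, pooled variance and no continuity correction, the normal approximation gives n = 20 per group with power 81.3%. The stated sample size reproduces. Exact power of the uncorrected chi-square test at n = 20 is 83.8%.

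**Hours left unobserved with one form.** Hour 0 is emergence, D the hour of discharge and C the hour the form is completed. The form covers C − 12 to C, and the period to be covered at home is D to 24:

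Gap = (24 − D) − max(0, min(C, 24) − max(D, C − 12))

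The documents give neither D nor C, so these are illustrations:

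| D | C | Gap (h) |
|---|---|---|
| 4 | 12 | 20 − (12 − 4) = 12 |
| 4 | 14 | 20 − (14 − 4) = 10 |
| 4 | 16 to 24 | 20 − 12 = 8 |
| 4 | 26 | 20 − (24 − 14) = 10 |
| 16 | 18 | 8 − (18 − 16) = 6 |
| 16 | 24 to 28 | 8 − 8 = 0 |
| 16 | 30 | 8 − (24 − 18) = 2 |

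The smallest gap over all C is max(0, 12 − D): 10 h at D = 2, 8 h at D = 4, 6 h at D = 6. It is zero for D ≥ 12, but only when 24 ≤ C ≤ D + 12.

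**Effect on the comparison (assumed inputs).** Take the outcome as any episode in 0–24 h. Let H be the share of cases sent home with a gap, and M the share of those whose only episodes fall in the gap. Then observed rate = true rate × (1 − H × M). The documents give neither H nor M. If nausea and vomiting prolong stay, H may be low. All results use the exact uncorrected chi-square test, two groups of 20, two-sided 5%.

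Equal losses, true rates 90% vs 50% (no loss: 83.8%):

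| H | M | Observed rates (%) | Difference (points) | Power |
|---|---|---|---|---|
| 10% | 10% | 89.1 vs 49.5 | 39.6 | 82.3% |
| 10% | 40% | 86.4 vs 48.0 | 38.4 | 77.7% |
| 25% | 10% | 87.75 vs 48.75 | 39.0 | 80.1% |
| 25% | 40% | 81.0 vs 45.0 | 36.0 | 67.9% |

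Unequal M, H = 25% in both arms, true rates 90% vs 50%:

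- M = 10% in the 90% arm and 40% in the 50% arm: 87.75% vs 45.0%, power 86.2%.
- The reverse: 81.0% vs 48.75%, power 59.4%.

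No true difference, 70% in both arms (rejection 5.3% with no loss):

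- M = 10% vs 40%, H equal in both arms: 5.6% at H = 10%, 6.7% at H = 25%, 10.2% at H = 50%.
- M = 40% in both arms, H = 10% vs 40%: 8.6%.

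**The case against.** The strongest reply is that the plan is under-specified rather than shown to lose data. The single form is an inference: the singular may name the instrument rather than a count, the form has date and time fields, and a caller may ask about the whole period since discharge. The day of the call is stated for same-day discharges. This stands as a limit on the claim: coverage is not ensured, but loss is not demonstrated. It does not remove the problem, because two families could both follow the protocol and report on different hours.

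The size is also open to challenge. H and M have no source in the documents, and the raised rejection rates need fourfold contrasts between arms that no text supports. At H = 10% the rejection rate is 5.6% against 5.3%, which is negligible. The loss that takes power below 80% depends on the method: about 2.5% of cases with the exact chi-square calculation, just under 1% with the normal approximation, while Fisher's exact test gives 74% before any loss. All of this stands, and the power figures are scenarios. The gap in hours needs neither H nor M.

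Two further points are fair. A form completed late also picks up episodes after hour 24 (at hour 30 it covers hours 18–30), which can raise observed rates. And the youngest children, from age 1, will have nausea reported by a parent, which a better-timed question does not cure.

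**Conclusion.** The concern holds. With one form, any discharge before hour 12 leaves at least 12 − D hours of the 24-hour window unobserved, whatever the timing. Later discharges are covered only if the form happens to be completed at a suitable hour. That follows from the form's recall period and the absence of a schedule.

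The effect on results cannot be fixed from the documents. It rests on assumed H and M, on taking any episode in 0–24 hours as the outcome (Section 8.0 does not define it), and on the power method. On the ranges used, equal losses cost about 1.5 to 6 points of exact power at H = 10% and about 4 to 16 points at H = 25%. Unequal losses can move the comparison either way. This should be fixed: hours that were not asked about cannot be recovered reliably later, and the remedy is cheap.

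**What to change.** In Section 5.0, for every child discharged before hour 24 after emergence:

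1. Make the follow-up call at or after hour 24, with the Rhodes form completed at hour 24 or as near to it as practical.
2. At that call, add one yes/no question: was there any nausea, retching or vomiting at any time between discharge and hour 24? This spans the gap for every discharge hour, whenever the form was filled in, and excludes episodes after hour 24. The chart review already collects "times of discharge from the recovery room to the floor and their discharge from the hospital", so the start of the period is known.
3. State that charted and home-reported episodes are counted together as any episode over the same 0–24 hour window.

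A second form at about hour 12, for children discharged before then, is needed only if Rhodes scores rather than yes/no occurrence are analysed. Overlapping hours must then not be counted twice.

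**Cost.** One added question, with recall of up to 24 − D hours (20 hours for discharge at hour 4, against 12 on the form), and parental report for the youngest. Call times are constrained: surgery late in the day means a late-afternoon or evening call. No second call or extra page is needed for yes/no occurrence, and nothing changes for children who stay 24 hours.
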